#### 3.2 Exclusion Criteria

List the criteria that define who will be excluded in your study.

#### Patient

- 1. enrolled in hospice and/or have a life expectancy of six months or less
- 2. admitted from a nursing home
- 3. no family caregiver to participate
- 4. mild cognitive impairment (CDR 0.5 without functional or ADL impairments)
- 5. severe dementia (CDR 3)
- 6. any significant neurological condition associated with cognitive impairment other than dementia (e.g. brain tumor)
- 7. a major acute psychiatric disorder

## Family caregiver

1. unable to recall at least two out of 3 words on the Three Word Recall

#### 3.3 Early Withdrawal of Subjects

#### 3.3.1 Criteria for removal from study

Insert subject withdrawal criteria (e.g., safety reasons, failure of subject to adhere to protocol requirements, subject consent withdrawal, disease progression, etc.).

#### For both patient and family caregiver:

- 1. Subject consent withdrawal
- 2. Death
- 3. Failure of subject to adhere to protocol

The Intent-To-Treat Principle will be followed to analyze data from the current proposed trial.

#### For the nurse/nurse champions:

1. Subject consent withdrawal

#### 3.3.2 Follow-up for withdrawn subjects

Describe when and how to withdraw subjects from the investigational product or study; the type and timing of the data to be collected for withdrawal of subjects; whether and how subjects are to be replaced; the follow-up for subjects withdrawn from investigational treatment.

If the participant withdraws from this study, already collected data will not be removed from the study database. The participant will be asked whether the investigator can collect data from his /her clinical records in the facility. If the individual agrees, this data will be handled the same as all other research data. Subjects will not be replaced.

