#### 7.4.2 Treatment Regimen

Describe dose, route of administration and treatment duration. Include information about dose adjustments.

The intervention begins during hospitalization. Post -acute follow-up will provide ongoing education and modification of the function-focused care plan (contact within 72 hours of discharge, weekly telephone calls for a total of 7 additional weeks, then monthly for 4 months).

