#### 7.4.5 Blinding of the Test Article

Describe how the test article is blinded.

To ensure comparable samples in both the treatment and control condition participants will be blinded to treatment arm prior to consent, since the Fam-FFC treatment requires more effort that the control condition.

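### Section 3.3.2 does not separate stopping Fam-FFC from leaving the study, and after withdrawal it seeks only facility records, which cannot supply the later H1–H3 outcomes

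*Combined protocol and SAP*

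**What the plan says.** Section 3.3.1 lists three grounds for removal of patients and caregivers: withdrawn consent, death, and "Failure of subject to adhere to protocol". Directly below, it adds: "The Intent-To-Treat Principle will be followed to analyze data from the current proposed trial".

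The template prompt in section 3.3.2 asks, among other things, for "the follow-up for subjects withdrawn from investigational treatment". The reply covers only a participant who withdraws from the study:

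- On data in hand: "already collected data will not be removed from the study database".
- On later data: "The participant will be asked whether the investigator can collect data from his /her clinical records in the facility".
- On replacement: "Subjects will not be replaced".

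Stopping the programme while staying in assessment is not mentioned.

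Section 7.4.2 gives the Fam-FFC post-discharge schedule as "contact within 72 hours of discharge, weekly telephone calls for a total of 7 additional weeks, then monthly for 4 months". The control condition in section 7.2 consists of caregiver information on hospital orientation and discharge teaching, and no post-discharge contact by the control nurse is described. Section 7.4.5 explains why participants are kept blind to arm until consent: "since the Fam-FFC treatment requires more effort that the control condition".

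The outcome tables in section 7.2 show where the H1–H3 data come from. The four caregiver scales are self-rated at T1, T2 and T3 only. Patient outcomes start at T0; under the COVID-19 procedure, those still collected after discharge are obtained from the caregiver by telephone or video. The monthly hospital-record check serves hospitalizations and emergency visits. Section 8.3 plans mixed models for Aims 1 and 2 and states no rule for outcomes missing after withdrawal.

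**The concern.** An intention-to-treat analysis needs outcomes from dyads that stop the intervention. The plan has no procedure to secure them, and the one source it names after withdrawal does not hold the outcomes behind H1–H3.

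The gap may not fall equally on the arms. Only Fam-FFC families have a continuing programme to tire of. A caregiver who says "no more calls" could be recorded as withdrawn at one site and kept in assessment at another, because nothing tells evaluators which is meant. If strained caregivers leave Fam-FFC while similar caregivers stay in control, Fam-FFC could look better on strain, burden and desire to institutionalize with no true effect. Outcomes missed in this way cannot be recovered later.

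**Working it through.** **1. What facility records could replace.**

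| Outcome | Source after discharge | In facility records? |
|---|---|---|
| H1: Barthel, return to baseline | Informant report | Not on schedule |
| H2: NPI-Q, CSDD, CAM | Informant or patient contact | Not on schedule |
| H2: chair rise, actigraphy | Direct measurement (dropped after discharge under the COVID-19 procedure) | No |
| H3: four caregiver scales | Caregiver self-report | No |
| H4: hospitalizations, emergency visits | Record check and family report | Yes, in part |

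**2. When a family could leave.** Scheduled Fam-FFC contacts after discharge: 1 + 7 + 4 = 12. T1 is due within 72 hours of discharge, as is the first contact, so 12 − 1 = 11 contacts fall after T1 is due. (T1 has a one-week window, so an early weekly call could still precede it.) Exits prompted by the calls therefore mainly cost T2 and T3. A caregiver who leaves in hospital or within days of discharge contributes nothing on the Aim 2 scales.

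**3. The plan's own allowance.** 73 × 6 = 438 and 146 × 3 = 438, so the total is consistent. Attrition of 20% is 0.20 × 438 ≈ 88 dyads, leaving about 350, or 175 per arm. Section 8.2 gives no numerical effect size. Back-solving with two-sided 0.05, 80% power and no clustering: d = (1.96 + 0.84) × √(2/175) ≈ 0.30. The allowance covers lost numbers. It does not cover unequal loss, and it includes deaths, so 88 is not an estimate of voluntary exits.

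**4. Size of bias if loss is unequal.** Assumptions, none of them in the documents: no true effect; T1, T2 and T3 strain trivariate normal with correlation 0.6; exit between T1 and T2 by a logistic rule with slope 0.7 to 1.5 per SD of strain (odds ratio e^0.7 ≈ 2.0 to e^1.5 ≈ 4.5). Exit is driven either by T1 strain, which is observed, or by T2 strain, which is not observed for leavers. The likelihood estimate uses T1 for everyone; clustering is ignored. The figures are the false Fam-FFC benefit at T3:

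| Exit, Fam-FFC v control | Likelihood estimate | Completers only |
|---|---|---|
| 8% v 2% | 0 to 0.02 SD | 0.02 to 0.04 SD |
| 25% v 15% | 0 to 0.03 SD | 0.04 to 0.06 SD |
| 20% v 5% | 0 to 0.04 SD | 0.05 to 0.10 SD |
| 30% v 10% | 0 to 0.06 SD | 0.08 to 0.13 SD |
| Equal rates, same exit rule | 0 | 0 |

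In the likelihood column, 0 is the result when T1 strain drives exit; the upper value needs unobserved T2 strain and the steepest slope. The completer column follows bias = (difference in loss) × (leaver–stayer difference in SD), for example (0.30 − 0.10) × 0.5 = 0.10 SD.

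The scenarios place exit after T1, so they do not size the loss from caregivers who leave before T1. Bias in H1 and H2 was not simulated.

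**The case against.** A reader might infer that leaving the study is the only way out of Fam-FFC, and that families who stop lose their H1–H3 outcomes. The documents do not support that.

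- No section says that declining FamPath or the nurse calls means leaving. Section 3.3.2 speaks only of withdrawal from the study.
- Section 3.1 sets the caregiver minimum at the initial assessment and development of FamPath, not the later calls. This is an eligibility criterion rather than an exit rule, but it fits families doing less and staying in.
- Sections 7.2 and 7.4.4 treat caregiver involvement and agreement with the plan as fidelity measures, so variable uptake is expected. The research nurse delivers Fam-FFC; separate evaluators, not told the allocation, collect outcomes.
- Data already collected are kept, including the pre-admission Barthel and T0 patient measures.

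A reader might also take the completer figures as the size of the problem. Section 8.3 plans mixed models, so the likelihood range is the relevant one.

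Differential loss is plausible but not shown. Section 2.2 reports pilot attrition and missing data below 5%, though the pilots were not randomized and their outcomes are reported to two months, not six. The direction is also open: Fam-FFC takes more effort but gives more support, and control families with little contact could leave more often.

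These points limit the finding but do not remove it. Section 3.3.2 is not merely silent: it states a rule for data after withdrawal, and that rule names a source that cannot serve H1–H3.

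**Conclusion.** The point holds as a gap in follow-up rules. The plan does not distinguish stopping Fam-FFC from leaving the study, and its rule for later data does not secure the outcomes its intention-to-treat statement needs. Mainly T2 and T3 are at risk. Aim 2 is the most exposed, because a caregiver lost before T1 has no value on any of its scales for a mixed model to use.

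The likely bias under the planned type of analysis is modest: about 0 to 0.06 SD in the assumed 20% v 5% and 30% v 10% scenarios. The upper end is 0.06/0.30 = one fifth of the back-solved detectable effect without clustering. The exit rates, the slopes, the correlation and the 0.30 are all assumptions. This is a worthwhile clarification, not a threat to the trial's validity as designed.

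Separately, removal for failure to adhere stands beside the intention-to-treat statement in section 3.3.1, and the two need to be reconciled.

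**What to change.** In section 3.3.2:

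1. State that a dyad that stops FamPath or the nurse calls is not thereby withdrawn. It stays in the T1–T3 assessments and is analysed in its assigned unit.
2. At any withdrawal, ask separately for (i) continued telephone assessment at the remaining T1–T3 points, (ii) clinical records, or (iii) neither. Record the choice by arm, so that unequal loss can be seen.

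Evaluators already make these contacts in both arms, and the COVID-19 procedure already provides for telephone collection. Telephone follow-up cannot recover chair rise or actigraphy, and some families will decline.

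The cost is a few extra calls and a protocol amendment. A consent line is needed only if the consent form, which was not available for this review, does not already offer the choice. Sites run in sequence and section 8.2 refers to the last site, so a late amendment would reach mainly later enrollees and retention rules would differ across sites. Both arms are present in each hospital, so the change would apply to both arms at the same time. Its date should be recorded.

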#### 4.0 Recruitment Methods

## 4.1 Identification of subjects

Describe the methods that will be used to identify potential subjects or the source of the subjects. If not recruiting subjects directly (e.g., database query for eligible records or samples) state what will be queried, how and by whom.

The Project Manager, research evaluators and PI will work with identified setting staff to provide us with a list of potentially eligible patients and recruit 146 patient/family caregiver dyads per participating setting (total sample 438 dyads). We are requesting a partial waiver to allow identification and, as appropriate, contact of potential participants to determine their interest in study participation. A flyer posted in the nursing station will alert/remind nursing staff of the study and ask them to refer potential study participants. It is the study staff's responsibility to ask permission of the patient to explain the study to the patient.

## 4.2 Recruitment process

Describe how, where and when potential subjects will be recruited (e.g., approaching or providing information to potential subjects for participation in this research study).

The research evaluators will provide IRB-approved information about the study/invitation to participate will to all potentially eligible patients/legally authorized representative (LAR) admitted to the study units (six medical or medical/surgical units of three hospitals in Pennsylvania). The patient and LAR will be approached to visit and discuss the study, and if granted, will receive: 1) brief oral information about the study; and 2) a copy of the consent form. The requirement to have a family CG (defined as the primary person providing oversight and support on an ongoing basis) involved and consented is explained to the patient/LAR. The patient and LAR may decide that another person, a CG other than the LAR, is the best person to participate in the study. In that case, that CG is provided information and if agreeable, engaged in the consent process.

Additionally, for the exploratory aim of assessing the cultural appropriateness of the intervention, we will recruit *family CGs* who self-identify as black, Latino, Asian and white, randomly selected from the Fam-FFC sample. Approximately 10 percent of families from each ethnic group represented in the study will be provided verbal information and approached for consent for participation in these interviews. Additionally, *the six nurse champions* will be consented and interviewed after the study ends in his/her particular unit/setting to provide their perspective on the cultural appropriateness of Fam-FFC. At the conclusion of the intervention at each site, approximately 6-8 *nurses* representing both shifts will be recruited to participate voluntarily in focus groups evaluating nurse-reported perceptions of: influence of nurse managers, organizational culture, likelihood of continuing to implement the intervention, and satisfaction. The purpose, voluntary nature, confidentiality, setting, time, and duration of the focus group will be shared with staff nurses at a staff meeting. If more than 8 nurses volunteer, we will accommodate their involvement by holding a second focus group.

## 4.3 Recruitment materials

List the materials that will be used to recruit subjects. Add recruitment documents to your study in CATS IRB (http://irb.psu.edu) on the "Consent Forms and Recruitment Materials" page. For advertisements, upload the final copy of printed advertisements. When advertisements are taped for broadcast, attach the final audio/video tape. You may submit the wording of the advertisement prior to taping to preclude re-taping because of inappropriate wording, provided the IRB reviews the final audio/video tape.

The data evaluator, responsible for recruitment, will provide information to all potential participants, using a flyer and verbal script. This information will be provided in person, and in some cases over the phone to family members who are not present.

#### 4.4 Eligibility/screening of subjects

If potential subjects will be asked eligibility questions before obtaining informed consent, describe the process. Add the script documents and a list of the eligibility questions that will be used to your study in CATS IRB (http://irb.psu.edu) on the "Consent Forms and Recruitment Materials" page.

Both patient and CG (who may or may not be the LAR) consent are required for the study process to proceed to screening. The research evaluator will check CG eligibility (able to recall at least two words on the Three Word Recall) in person or over the phone, and then screen the patient in person for dementia using the Montreal Cognitive Assessment (MoCA)  and AD8.  Patients who screen positive for dementia will then be assessed for severity of dementia using the Clinical Dementia Rating (CDR). A diagnosis of very mild to moderate stage dementia as confirmed by a score of 0.5 to 2.0 on the Clinical Dementia Rating Scale will be required. Functional ability will be assessed with the Pfeffer Functional Activities Questionnaire (FAQ) to discriminate MCI from dementia.

## 5.0 Consent Process and Documentation

Refer to "SOP: Informed Consent Process for Research (HRP-090)", for information about the process of obtaining informed consent from subjects. HRP-090 can be accessed by clicking the Library link in CATS IRB (http://irb.psu.edu).

#### 5.1 Consent Process

#### **5.1.1** Obtaining Informed Consent

## 5.1.1.1 Timing and Location of Consent

Describe where and when the consent process will take place.

The consent process of patient/family caregiver dyads will occur within 48 hours of admission to the unit. Patients will be consented in person. The family caregivers will also be consented in person unless they are unable to be present with the research staff within the 48- hour timeframe, in which case they will be consented over the telephone. Nurse champions will be consented at the beginning of the study, prior to patient/family caregiver enrollment. Hospital staff nurses will be consented for post-intervention focus groups at the conclusion of the intervention. All consenting will occur within a private setting.

#### 5.1.1.2 Coercion or Undue Influence during Consent

Describe the steps that will be taken to minimize the possibility of coercion or undue influence in the consent process.

Patient/family caregivers will be informed about the study. Research staff are trained to give sufficient time for answers and questions and to offer to come back/give extra time for consideration. Because the focus of this study is partnership with the family caregiver to improve the care /outcomes of persons with dementia, we will inform patients/families that in order to be eligible to participate, both members of the dyad need to assent or consent. If one member of the chooses not to participate, we don't enroll the dyad, and assure them that there are no negative sequelae associated with this decision.

Both patient/family caregivers will need to pass the Evaluation to Sign Consent to fully consent. This will assure that they understand what they are volunteering to participate in the study. Both patient and family caregivers will be informed that the decision to participate or not will have no bearing on the care and services provided by the hospital to both patient and family caregivers.

We will provide a \$20 gift certificate at three time points during the study, at discharge from the hospital, at the second post-discharge data collection, and upon conclusion of the study. The two

different time-periods and modest nature of this honorarium offset the potential for undue influence.

The inclusion of nurse champions and staff nurses in the study is purely voluntary. Those who volunteer will be consented. All staff will be informed that their decision to participate or not will not in any way influence their working conditions or standing.

#### 5.1.2 Waiver or alteration of the informed consent requirement

If you are requesting a waiver or alteration of consent (consent will not be obtained, required information will not be disclosed, or the research involves deception), describe the rationale for the request in this section. If the alteration is because of deception or incomplete disclosure, explain whether and how subjects will be debriefed. Add any debriefing materials or document(s) to your study in CATS IRB (http://irb.psu.edu) on the "Supporting Documents" page. NOTE: Review the "CHECKLIST: Waiver or Alteration of Consent Process (HRP-410)" to ensure you have provided sufficient information for the IRB to make these determinations. HRP-410 can be accessed by clicking the Library link in CATS IRB (http://irb.psu.edu).

n/a

#### 5.2 Consent Documentation

#### 5.2.1 Written Documentation of Consent

Refer to "SOP: Written Documentation of Consent (HRP-091)" for information about the process to document the informed consent process in writing. HRP-091 can be accessed by clicking the Library link in CATS IRB (http://irb.psu.edu).

If you will document consent in writing, describe how consent of the subject will be documented in writing. Add the consent document(s) to your study in CATS IRB (http://irb.psu.edu) on the "Consent Forms and Recruitment Materials" page. Links to Penn State's consent templates are available in the same location where they are uploaded and their use is required.

The following participants will be consented: 1) patient and CG, 2) nurse champions, and 3) nurses.

Both patient and CG consent are required. After information is provided, and the patient and CG agree to participate, an evaluation of capacity to provide consent will be conducted, using the Evaluation to Sign Consent (ESC). 131 If capacity is determined the patient may provide his or her own consent. If decisional capacity is impaired, and the patient provides assent, the LAR will complete the consent process. The legally authorized representative will be encouraged to try and determine what the patient would do if competent and base his/her decision upon what he/she thinks is in the patient's best interest. The CG's ability to sign consent will also be evaluated using the ESC. Only CGs answering all ESC questions correctly will be enrolled. Both patient and CG (who may or may not be the LAR) consent are required for the study process to proceed to screening. The consenting party is requested to sign the consent form. If it is not possible to obtain written signature from the LAR, verbal consent may be documented. The research evaluator will check CG eligibility (including the ability to recall at least two words on the Three Word Recall) and then screen the patient for dementia using the Montreal Cognitive Assessment (MoCA) 123 and AD8. 128 Patients who screen positive for dementia will then be assessed for severity of dementia using the Clinical Dementia Rating (CDR). A diagnosis of very mild to moderate stage dementia as confirmed by a score of 0.5 to 2.0 on the Clinical Dementia Rating Scale will be required. Functional ability will be assessed with the Pfeffer Functional Activities Questionnaire (FAQ) to discriminate MCI from dementia. 132

Prior to the study the PI will ask the unit manager of the three intervention units to identify two nurse champions (to cover both nursing shifts). The PI will emphasize that the nurse champions must be

volunteers, in order to support their right to refuse without losing any job standing, as well as to support the success of the study. The PI will meet with the prospective nurse champions in private, explain the purpose of the study, procedures, possible risks and benefits, time commitment, compensation, privacy/confidentiality, payment, PI contact information, and voluntary nature of the research, including the interview that will be conducted at the end of the study. If the nurse declines to participate as champion, another potential participant will be recruited and asked to provide an informed consent. A total of six nurse champions will be recruited.

At the end of the study at each of the three hospital cites, the PI will attend a staff meeting on the three intervention units. The PI will explain the plan for focus groups to obtain nurses' feedback on the effectiveness and sustainability of the intervention. Staff nurses will receive information on the focus groups and asked to participate. The nurses will receive information about the purpose, procedures, possible risks and benefits, time commitment, compensation, privacy/confidentiality, payment, PI contact information, and voluntary nature of the research

All participants will receive a copy of the consent to keep for future reference.

